3 OVERALL STUDY DESIGN

The METIMMOX study is a multicenter open-label randomized phase 2 trial in first-line treatment of MSS metastatic CRC using the standard-of-care Nordic FLOX regimen (control arm) or sequential therapy with the Nordic FLOX regimen and nivolumab (experimental arm), to investigate whether the experimental arm shows superiority in PFS, safety, tolerability, and QoL.

Study period

Estimated date of first patient enrolled: 1 March 2018
Anticipated recruitment period: 12 months
Estimated date of last patient completed: 1 September 2020

Treatment duration

Expected treatment duration per patient:
Experimental arm: 18 months (until failure of treatment strategy)
Control arm: 9 months (until failure of treatment strategy)

Follow-up

Expected follow-up period per patient:
Experimental arm: 30 months (12 months following failure of treatment strategy)
Control arm: 21 months (12 months following failure of treatment strategy)

4 STUDY POPULATION

4.1 Selection of study population

Centers across Norway will participate. The Institutions are:

- Akershus University Hospital, Lørenskog, Norway (catchment population of 500,000).
- St. Olavs Hospital – Trondheim University Hospital, Trondheim, Norway (catchment population of 450,000).
- Haukeland University Hospital, Bergen, Norway (catchment population of 450,000).
- Hospital of Southern Norway, Kristiansand, Norway (catchment population of 290,000).
- Oslo University Hospital, Oslo, Norway (catchment population of 500,000).

All citizens of Norway have equal access to public health services. As a consequence, there will be no selection of patients onto the METIMMOX study other than that based on specific inclusion and exclusion criteria. This population-based study accrual will provide a unique opportunity to investigate the generalizability of the study concept across a majority of patients with metastatic CRC. Importantly, algorithms for personalized allocation of first-line treatments in patients with metastatic CRC are uniform across Scandinavian countries and also incorporated in the respective national guidelines for management of CRC. Finally, there is no other study currently planned for this CRC population that might compete for patients.

As seen from the above list of Institutions, the total catchment population from the participating Norwegian centers is close to 2.2 million, or more than 40% of the nation's population. It is therefore reasonable to assume an annual figure of almost 850 metastatic CRC cases among these centers. Therefore, if the study manages to enroll well over one tenth of these patients, the study accrual phase should last approximately one year.

This project will actively use the Norwegian Clinical Research Infrastructures Network (www.norcrin.no) and their resources in the planning for and conducting the study. For example, this enables the access to the Viedoc system, which includes web-based case report forms (CRF) with an ancillary eDatabase, randomization procedures, and validation of data, along with study monitoring, all of which meet regulatory requirements for clinical therapy trials.

4.2 Number of patients

100 patients will be included in this trial (50 in each study arm).

4.3 Inclusion criteria

All the following conditions must apply to the prospective patient at screening prior to receiving study treatment:

- Patient has histologically verified CRC adenocarcinoma (also comprising the mucinous adenocarcinoma and signet-ring cell carcinoma entities).
- Patient is ambulatory with Eastern Cooperative Oncology Group (ECOG) performance status 0 or 1 (*c.f.*, **Appendix 4**).
- Patient is at least 18 years of age.
- Patient has radiologically measurable metastatic disease.
- Patient has an intra-abdominal metastatic lesion that can be biopsied.
- Patient has not had previous systemic therapy for the metastatic disease.
- Patient is eligible for the Nordic FLOX regimen.
- Patient has the following laboratory values, as measured in serum/plasma within 14 days prior to study entry, indicative of adequate organ function:
 - Hemoglobin at least 10.0 g/dL.
 - Neutrophils at least $1.5 \times 10^9/L$ (without current use of colony-stimulating factors).
 - Platelets at least $100 \times 10^9/L$.
 - C-reactive protein less than 60 mg/L.
 - AST/ALT no higher than 2xULN when patient does not have metastatic disease in the liver or no higher than 5xULN when patient has metastatic disease in the liver.
 - Bilirubin no higher than 1.5xULN when patient does not have metastatic disease in the liver or no higher than 2xULN when patient has metastatic disease in the liver.
 - Albumin no lower than 30 g/L.
 - INR within normal level.
 - Creatinine no higher than 1.5xULN.
- Woman of childbearing potential (WOCBP)³ must have a negative serum or urine pregnancy test (minimum sensitivity 25 IU/L or equivalent units of HCG) within 24 hours prior to the start of study drug.
- WOCBP will use an adequate method⁴ to avoid pregnancy for a period of 26 weeks (which includes the required 30 days plus the time required for nivolumab to undergo five half-lives) after the last therapy dose, irrespective of study arm.
- Woman is not breastfeeding.

- Male who is sexually active with WOCBP must agree to follow instructions for method(s) of contraception⁴ for a period of 26 weeks (which includes the required time to ensure duration of sperm turnover plus the time required for the investigational drugs to undergo five half-lives) after the last therapy dose, irrespective of study arm.
- Signed informed consent form (ICF) and expected cooperation of the patients for the treatment and follow-up must be obtained and documented according to International Conference on Harmonization (ICH) – Good Clinical Practice (GCP) and national/local regulations.

³ **WOCBP** is defined by the Clinical Trial Facilitation Group's document "Recommendations related to contraception and pregnancy testing in clinical trials" version 2014-09-15 (http://www.hma.eu/fileadmin/dateien/Human_Medicines/01-About_HMA/Working_Groups/CTFG/2014_09_HMA_CTFG_Contraception.pdf). A woman is considered WOCBP, i.e., fertile, following menarche and until becoming post-menopausal unless permanently sterile. Permanent sterilization methods include hysterectomy, bilateral salpingectomy, and bilateral oophorectomy. A postmenopausal state is defined as no menses for 12 months without an alternative medical cause. A high follicle-stimulating hormone level in the postmenopausal range may be used to confirm a postmenopausal state in women not using hormonal contraception or hormonal replacement therapy. However, in the absence of 12 months of amenorrhea, a single measurement of the follicle-stimulating hormone level is insufficient.

⁴ **Highly effective birth control methods** are defined by the same recommendations. They include:

- Combined (estrogen- and progesterone-containing) hormonal contraception associated with inhibition of ovulation:
 - oral
 - intravaginal
 - transdermal
- Progesterone-only hormonal contraception associated with inhibition of ovulation:
 - oral
 - injectable
 - implantable
- Intrauterine device
- Intrauterine hormone-releasing system
- Bilateral tubal occlusion
- Vasectomized partner
- Sexual abstinence

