10 STATISTICAL METHODS AND DATA ANALYSIS

10.1 Determination of sample size

Calculation of sample size was performed for PFS – the primary end point – and based on PFS data from recent publications. A median PFS of 9 months was assumed for the standard-of-care (control arm) [Cartwright, 2012; Tveit *et al.*, 2012; Cremolini *et al.*, 2015]. Regarding the therapy concept of ICB, there is no PFS data published as yet for the setting of interest. In the study of patients with treatment-refractory metastatic CRC, median PFS was not reached in the cohort with mismatch repair-deficient disease at the time of reporting [Le *et al.*, 2015]. In the study of previously untreated patients with advanced non-small cell lung cancer, which is a tumor entity with considerably poorer prognosis than advanced CRC, patients with PD-L1-positive tumors that were randomized to ICB showed median PFS of 10.3 months compared to 6.0 months for standard chemotherapy [Reck *et al.*, 2016].

Extrapolating to the setting of interest, with a median PFS of 9 months for standard-of-care, a median PFS twice as long (18 months) was entered for the sequential therapy. Assuming the exponential distribution of survival functions, the median PFS estimates were converted to hazard ratio (HR) of 0.5. Allowing for 10% censoring rate of subjects, the required sample size was estimated to be 40 patients in each arm to be able to show that HR of 0.5, implying the risk of a PFS event in the experimental group is 50% lower than in the control group, is significantly different from 1 with the power of 80% at significance level of 5%, given that log-rank test will be used.

However, it was necessary with several adjustments of the above calculations to maintain sufficient power. First, the sample size was adjusted to enable removal of a maximum of 5% enrolled cases with non-MSS tumor before data analysis. Next, keeping in mind the condition of patients, it is not unlikely that some will be lost from the study before a valid PFS event has been reached. Also, a number of analyses stratified by primary tumor sidedness and (K)RAS/BRAF mutation status will be performed. Hence, to enable high enough power in the statistical analysis, the sample size was increased by an additional 20%. After incorporating the adjustments, the final sample size was estimated to be 100 patients, 50 in each arm, with 1:1 randomization.

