#### 4.5. Baseline patient characteristics

Continuous baseline characteristics will be presented as means and standard deviations or as medians and minimum and maximum dependent on the distribution. Categorical data will be presented by frequencies and percentages. Baseline characteristics will be presented by intervention and control groups. Following characteristics will be presented: age, sex, ECOG performance status, primary tumor sidedness, tumor (K)RAS/BRAF mutation status, number of metastatic sites, and if the liver is involved or not.

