#### 5.2. Analysis methods

*Main statistical analyses.* The main statistical analysis is planned after the last patient has fulfilled the pre-defined follow-up period. PFS will be calculated from the day of randomization to first recorded disease progression according to RECIST v1.1 or when applicable iRECIST, or death. Patients who have not had disease progression at the time of final analysis will be censored at the date last known to be alive and progression-free. The analyses will compare the treatment groups in total as well as groups stratified by primary tumor sidedness and (K)RAS/BRAF mutation status.

*Interim analyses.* Interim analyses will apply to data on safety, tolerability, possible detrimental effects, and curative outcomes, and will be based on purely clinical judgment by the External Data and Safety Monitoring Committee. These types of data will be reported as the number of events.

*Descriptive statistics.* Demographic and clinical characteristics will be presented as means and standard deviations, medians with minimum and maximum values, or frequencies and percentages, as appropriate. Further statistical analyses will be separated to primary analyses, including only comparison of primary end point between two treatment arms, and secondary analyses, including stratified analyses on primary and secondary end points as well as number of analyses on secondary end points.

*Primary analysis.* Median PFS time will be compared between study arms by drawing Kaplan-Meier survival curves and performing log-rank test. HR with the corresponding 95% CI and p-values will be estimated by Cox proportional hazards model.

*Secondary analyses.* Distribution of PFS times stratified by the primary tumor sidedness and (K)RAS/BRAF mutation status will be illustrated graphically by Kaplan-Meier curves and compared by log-rank test. To assess the hazard rates for disease progression within each strata, Cox proportional hazards model will be estimated and, if appropriate, adjusted for relevant covariates. The results will be presented as HR with the corresponding 95% CI and p-values.

Safety. The number of serious adverse events (SAE) will be summarized and presented by trial arm. In addition, information will be given on the number of SAE per participant, together with details on the causality, expectedness, and outcome of each SAE experienced. Summaries of suspected unexpected serious adverse reaction (SUSAR) events will also be presented by trial arm.

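### ECOG status, number of metastatic sites and liver involvement are recorded at baseline but named in no efficacy model; prespecified adjustment of the PFS hazard ratio would add some power at almost no cost

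*Protocol*

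**What the plan says.** **Who enters.** Protocol 4.3 requires that "Patient is ambulatory with Eastern Cooperative Oncology Group (ECOG) performance status 0 or 1". SAP 4.2 accepts liver, peritoneal and/or nodal disease. Patients can therefore differ in performance status, in number of metastatic sites and in whether the liver is involved.

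**What is recorded.** The SAP 4.5 baseline list includes ECOG and ends with "number of metastatic sites, and if the liver is involved or not".

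**What randomisation controls.** Protocol 10.2.1 and SAP 2.2 stratify by sidedness and (K)RAS/BRAF status only.

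**What the models contain.**
- Primary PFS (protocol 10.4.4, SAP 5.2): Kaplan-Meier curves, a log-rank test, and "HR with the corresponding 95% CI and p-values will be estimated by Cox proportional hazards model". No covariate is named.
- Secondary PFS within strata (protocol 10.4.5, SAP 5.2): a Cox model that may be adjusted where judged suitable. The covariates are not listed.
- ORR and SSCRR (logistic), DOR and OS (Cox): adjusted for the stratification factors only.
- SAP 5.4 plans nothing further.

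**The concern.** The three values will be in the database whatever the analysis plan says. If they are prognostic for PFS, a comparison that ignores them has two costs. It gives up some power that adjustment would recover. It also leaves the single HR from a 100-patient trial exposed to whatever imbalance chance produces.

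The optional clause for the within-stratum model does not close the gap. It does not reach the primary comparison, and it leaves the choice of covariates open. If the baseline table shows an imbalance, any adjustment chosen at that point is post hoc and open to challenge, whichever way it moves the result.

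**Working it through.** **1. The plan's own figure.** Protocol 10.1 states that "the median PFS estimates were converted to hazard ratio (HR) of 0.5", from medians of 9 and 18 months, and asks for a result "significantly different from 1 with the power of 80% at significance level of 5%, given that log-rank test will be used". Sidedness of the test is not stated; two-sided reproduces the figure.
- Freedman: events = (1.96 + 0.84)² × (1 + 0.5)² / (1 − 0.5)² = 7.85 × 9 = 70.6, so 71.
- With 10% censoring: 71 / 0.9 = 78.9, so 40 per arm. This matches "Allowing for 10% censoring rate of subjects, the required sample size was estimated to be 40 patients in each arm".
- Inflation: 5% because "the sample size was adjusted to enable removal of a maximum of 5% enrolled cases with non-MSS tumor before data analysis", then "the sample size was increased by an additional 20" per cent: 80 × 1.05 × 1.20 = 100.8, against 100 stated.

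The base design reproduces.

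**2. Power of the unadjusted test at the enrolled size.** With 100 patients and 90 events, Freedman gives Φ(√90 × 0.5/1.5 − 1.96) = Φ(1.20) = 88.5%. Schoenfeld gives 90.8%. With 95 patients after removal of non-MSS cases (85.5 events), the figures are 86.9% and 89.3%. All exceed 80%.

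**3. Gain from adjustment (assumption-based).** The documents give no prevalence or prognostic HR for the three factors. Assumed: independent binary factors, exponential PFS, 50 per arm, unadjusted treatment HR about 0.5, Wald tests. The two-factor runs use prevalences of 40% and 50%, 10% censoring and 1,500 trials per setting. The three-factor runs use 40%, 50% and 70%, about 87 to 91 events and 2,500 trials.

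| Prognostic HR, each factor | Two factors: unadjusted v adjusted power | Three factors: unadjusted v adjusted power |
|---|---|---|
| 1.2 | 90% v 89% | not run |
| 1.3 | 87% v 88% | 91.4% v 92.6% |
| 1.5 | 87–88% v 90–91% | 90.1% v 94.0% |
| 2.0 | 88% v 94–95% | 90.2% v 96.8% |
| 2.5 | 89–90% v 98% | not run |

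Ranges show two independent sets of trials. The gain over prognostic HRs of 1.3 to 2.5 is about 0 to 9 points. With three factors of almost no effect (HR 1.01), adjustment changed power by −0.7 points at 100 patients and −1.1 at 95.

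The gain does not come from a narrower interval. In the three-factor run at HR 1.5, the SD of the log HR was 0.219 unadjusted and 0.229 adjusted, while the mean HR was 0.497 and 0.460. The signal-to-noise ratio is ln(0.497)/0.219 = −3.19 against ln(0.460)/0.229 = −3.39.

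**4. Type I error.** With no treatment effect, three factors and 3,000 trials, rejection was 5.1% and 5.4% unadjusted, and 5.8% and 5.7% adjusted (prognostic HR 1.5 and 2.0).

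**5. Chance imbalance.** With ECOG 1 in an assumed 40%, the SD of the arm difference is √(2 × 0.4 × 0.6 / 50) = 0.098, so 2 SD is about 20 percentage points. The HR moves by a factor of exp(0.196 × ln prognostic HR):
- prognostic HR 1.5: 1.08
- prognostic HR 2.0: 1.15
- prognostic HR 2.5: 1.20

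For scale, the standard error of the log HR at 90 events is about 2/√90 = 0.211. The log shifts of 0.080, 0.136 and 0.180 are 0.38, 0.64 and 0.85 of it.

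For all three factors together, Σp(1 − p) = 0.24 + 0.25 + 0.21 = 0.70 and the SD is √(0.70 × 2/50) = 0.167. A 1.96-SD imbalance gives factors of 1.09, 1.14 and 1.26 for prognostic HRs of 1.3, 1.5 and 2.0.

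**The case against.** The best defence is that an unadjusted primary analysis is legitimate in a randomised phase 2 trial and that the design loses nothing it promised. The HR of 0.5 was converted from arm medians, so it is an unadjusted HR, and the sample size rests on the log-rank test. That stands. It is the reason to keep the log-rank test as primary rather than replace it with an adjusted p-value.

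Three stronger readings are tempting, and the documents do not support them.

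- *That these factors can enter no model at all.* The within-stratum PFS model may be adjusted for unnamed covariates. The gap is that nothing is prespecified and the primary model is untouched.
- *That the trial forfeits a double-digit share of its power.* A gain of about 12 to 13 points appears at 40 per arm with two factors at HR 2.5 each. At full size it needs three independent factors at HR 2.0 with 0.5 read as the covariate-conditional HR; unadjusted power is then about 74 to 76%. The trial enrols 50 per arm, and the design HR is not a conditional one.
- *That the unadjusted HR is biased.* Imbalance is random in direction and is already part of the sampling error that the interval describes. The unadjusted HR lies closer to 1 than the adjusted HR because the two estimate different quantities.

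**Conclusion.** The point holds as a matter of efficiency and prespecification. Three baseline values that will be collected anyway are named in no efficacy model, and the one clause that could admit them is optional, unnamed and secondary.

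The expected benefit of adjustment is about 0 to 9 points of power, against a loss of about 1 point if the factors carry no information. The size depends entirely on assumed prognostic HRs (1.3 to 2.5), assumed prevalences and independence between factors. Correlated or weaker factors would sit at the low end. The simulations did not include the two stratification terms.

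Validity is not in question, and the stated 80% power is met without adjustment when 0.5 is the unadjusted HR. The change is worth making, but the plan does not fail without it.

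**What to change.** In SAP 5.2 and protocol 10.4.4, before database lock:

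- Keep the log-rank test as the planned primary test.
- State that the PFS HR and 95% CI will also be reported from a Cox model with treatment, ECOG (0 v 1), number of metastatic sites (1 v 2 or more), liver involvement (yes/no), sidedness and (K)RAS/BRAF status, with the unadjusted HR beside it.
- Use the same covariates for OS.

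The cost is a few lines of SAP wording and no new data. Protocol 10.4.1 allows the plan to be amended until database lock. The model has six terms, so 71 to 90 PFS events give 71/6 = 11.8 to 90/6 = 15 events per term, which is workable. The small downside is that the adjusted HR is conditional on the covariates and so is not directly comparable with the design HR of 0.5. Showing both estimates deals with that.

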4.4 Exclusion criteria

Patient will be excluded from the study if she/he meets any of the following criteria:

- Patient has initially resectable metastatic disease for which neoadjuvant therapy is deemed superfluous.
- Patient does not consent to biopsy sampling.
- Patient has metastatic disease to lungs as the sole site.
- Patient has untreated or symptomatic brain metastasis (patient must be symptom-free without the use of corticosteroids).
- Patient has experienced a period of less than 6 months since discontinuation of adjuvant oxaliplatin-containing chemotherapy.
- Patient is ineligible for full chemotherapy doses (100% doses) at start of study treatment.
- Patient has had radiation therapy against the only measurable lesion within 4 weeks of start of study treatment.
- Patient has a medical condition treated with anticoagulant medication that cannot be replaced by low molecular weight heparin during active study treatment.

- Patient has a nervous system disorder worse than CTCAE grade 1.
- Patient has any medical condition that will preclude him/her from cancer immune-modulating therapy, such as:
 - Active or chronic hepatitis B or hepatitis C.
 - Known history of human immunodeficiency virus or acquired immunodeficiency-related illnesses.
 - Diagnosis of immunodeficiency or medical condition requiring systemic steroids or other forms of immunosuppressive therapy.
 - Autoimmune disease that has required systemic therapy within the past 2 years.
 - Receipt of live attenuated vaccination within 30 days prior to study entry or within 30 days of receiving study therapy.
 - Active infection or chronic infection requiring chronic suppressive antibiotics.
 - Known history of previous diagnosis of tuberculosis.
- Patient with current or prior use of immunosuppressive medication within 28 days before the first dose of study therapy, with the exceptions of intranasal corticosteroids or systemic corticosteroids at physiological doses that do not exceed 10mg/day of prednisone or an equivalent corticosteroid.
- Patient has any medical condition or needs to use medication, as listed in the SmPC of each Investigational Medical Product (IMP), that will preclude him/her from receiving treatment with IMP, such as:
 - Pernicious anemia or anemias due to vitamin B₁₂ deficiency (SmPC-listed contraindications for folinic acid).
 - Other SmPC-listed contraindications for folinic acid and SmPC-listed contraindications for the other IMPs are covered by other exclusion criteria.
- Patient has undergone treatment with any IMP that may interfere with the study treatment within 4 weeks prior to first administration of study drug.
- Patient has known hypersensitivity to any of the study IMP components.
- Patient has ECOG performance status 2 or worse.
- Patient has serum/plasma CRP of 60 mg/L or higher.
- Patient does not meet the following requirements at baseline: adequate bone marrow function without current use of colony-stimulating factors (minimum values of neutrophils $1.5 \times 10^9/L$, platelets $100 \times 10^9/L$, hemoglobin 10 g/dL), adequate liver function (maximum values of AST/ALT 5xULN and bilirubin 2xULN; albumin value of 30 g/L or higher; INR within normal level), adequate renal function (maximum creatinine value of 1.5xULN).
- Patient has history of other prior malignancy, with the exception of curatively treated basal cell or squamous cell carcinoma of the skin, cervical cancer stage IB, stage I prostate cancer considered not necessary to treat, and another malignancy that was treated with curative intent more than 5 years ago and has not relapsed later.
- Patient has significant cardiac, pulmonary, or other medical illness that would limit activity of daily life (ADL) or survival.
- Patient is pregnant or breastfeeding.
- Patient has any other reason, in the opinion of Clinical Investigator, not to participate in the study.

